3. INVESTIGATIONAL PLAN

3.1. Overall Study Design

This is a first-in-human, randomized, placebo-controlled, 6-Part, SAD and MAD study in healthy adult subjects, adult subjects with CG, and adult subjects with GALK-deficient Galactosemia. The study will assess the safety and PK of AT-007 in these subjects as well as the effect of AT-007 on biomarkers of galactose metabolism (galactose and galactose metabolites) in subjects with galactosemia. The study is being conducted in multiple centers in the US and Europe. This study consists of 6 parts ([Table 1](#)) with the timing of the parts as shown in [Figure 2](#).

Table 1: Study Design

[figure not shown]
Study Part	Study Population	Design	Planned Number of Cohorts	Subjects Per Cohort	Total # of Subjects
Part A	Healthy Adult Subjects	SAD	5	8	40
Part B	Healthy Adult Subjects	MAD (QD for 7 days)	4	6 in 2 cohorts & 8 in 2 cohorts	28
Part C	Healthy Adult Subjects	MAD (QD for 7 days)	3	4	12
Part D	Adult Subjects with CG	SAD, 5-day washout, MAD (QD for 27 days)	3	6	18
Part E	Adult Subjects with GALK-deficient Galactosemia	SAD, 5-day washout, MAD (QD for 27 days)	1 to 3	6	18
Part D Extension	Adult Subjects with CG	MAD (QD for 90 Days)	1 to 2	8 to 28	28

CG = Classic Galactosemia; EOS = end of study; MAD = multiple ascending dose; QD = once daily (dosing); SAD = single ascending dose; TEAE = treatment emergent adverse event.

The total number of subjects column reflects the maximum number of subjects if all cohorts are conducted with the planned number of subjects and no subject participates in more than 1 cohort and/or part. However, in Parts D and E, subjects are allowed to participate in multiple cohorts (assuming no safety or tolerability issues in the prior cohort) on any treatment assignment with a \geq 5-day washout period between the last dose of study drug in one cohort and the first dose of study drug in the next cohort. Also, Part D subjects can participate in Part D Extension at any time after the Part D EOS Visit (Part D completers and those who discontinued for any reason other than study drug related TEAE and had an EOS Visit more than 14 days after the last dose) or any time beyond 14 days after the last dose in Part D (Part D subjects who discontinued Part D for any reason other than study drug related TEAE and did not have an EOS Visit more than 14 days after the last dose).

Parts A and B are double-blind. Part C is open-label. In Parts D, E, and D Extension, the clinical site staff (except for the unblinded pharmacist) and the subjects are blinded to study treatment but the Sponsor is not blinded.

The number of cohorts and total number of subjects may increase if doses > 40 mg/kg are tested in additional cohorts (see [Section 1.4](#)). Also, in Parts D and E, the overall number of subjects per cohort may be increased up to 8 subjects to address any potential lost-to-follow-up among subjects treated with either placebo or AT-007. Up to 28 total subjects in up to 2 cohorts are planned for Part D Extension.

Figure 2: Study Schematic

Within each Part, the Cohorts are sequential. Solid lines with arrows indicate that data from the part or cohort at the non-arrow end are required before the part or cohort at the arrow end can start. Dotted lines indicate cohorts (C1 and B3; C3 and B4) that will be conducted simultaneously. Parts D, E, and D Extension are not dependent on Part C results, and no temporal relationship between Parts D, E, and D Extension and Part C is implied. Also, with the exception of Cohorts B4, C3, D3, E2, E3, and DE2 being directly or indirectly dependent on Cohort A5 results, no temporal relationship between Cohort A5 and any other part/cohort is implied. Cohort DE2 (start and dose level) are not dependent on results from Cohort DE1. Figure is not to scale.

Parts A, B, and C are being conducted in a single clinical research unit (CRU) in the US. Subjects within each cohort in Part A were enrolled and dosed at approximately the same time (within 2 to 3 days for the first cohort and on the same day for the subsequent cohorts). Subjects within each cohort in Part B will be enrolled and dosed on the same days. The first cohort of Part C (C1) was conducted simultaneously with the third cohort of Part B (B3) and received the same dose (10 mg/kg) as the second cohort of Part B (B2). The second cohort of Part C (C2) started after all subjects in the third cohort of Part B (B3) completed the study (minus the End-of-Study [EOS] Visit) and received the same dose (20 mg/kg) as Cohort B3; safety and PK results for Cohort C1 were also considered before starting Cohort C2. The third cohort in Part C (C3) will be conducted simultaneously with the fourth cohort of Part B (B4) and receive the same dose (40 mg/kg); safety and PK results for Cohort C2 were also considered before starting Cohort C3. For Cohorts B3 and C1, subjects were enrolled and dosed on the same day but in different parts of the CRU to separate double-blind (B3) from open-label (C1) dosing. All subjects in Cohort C2 were enrolled and dosed on the same day. All subjects in Cohorts B4 and C3 will be enrolled and dosed on the same day but in different parts of the CRU to separate double-blind (B4) from open-label (C3) dosing.

Parts D, E, and D Extension are being conducted in multiple CRUs. It is not anticipated that subjects within each cohort will be enrolled/dosed at approximately the same time.

Initially, 4 double-blind dosing cohorts were planned in the SAD portion of the study in healthy subjects (Part A); subsequently, a fifth cohort (A5) was added to Part A. Within each cohort of 8 subjects, 6 subjects were randomly assigned to AT-007 and 2 subjects were randomly assigned to placebo. For the first cohort, the first 2 subjects were sentinel subjects with 1 subject randomly assigned to AT-007 and 1 subject randomly assigned to placebo. These 2 sentinel subjects were observed for at least 24 hours before any of the additional subjects (6 subjects: 5 randomly assigned to AT-007 and 1 randomly assigned to placebo) in the first cohort were dosed. The dose levels of AT-007 for Cohorts A1, A2, A3, A4, and A5 were 0.5, 5, 10, 20, and 40 mg/kg.

Before the study proceeded to Part B (MAD in healthy subjects), safety data from Cohorts A1 through A4 in Part A (SAD in healthy subjects) were evaluated by the Safety Review Committee (SRC) ([Section 3.4](#)) and all PK data from Cohorts A1 through A4 were evaluated by the Sponsor. As of this protocol version, Cohorts A1 through A5 (0.5, 5, 10, 20, and 40 mg/kg) have completed the study with acceptable results.

Four double-blind dosing cohorts are planned in the MAD portion of the study in healthy subjects (Part B). Within each cohort of 6 or 8 subjects, 4 or 6 subjects will be randomly assigned to AT-007 and the remaining 2 subjects will be randomly assigned to placebo. Subjects will receive study drug (AT-007 or placebo) QD for 7 consecutive days. The starting dose level of AT-007 for the first cohort (B1) was 5 mg/kg based on the results of Part A. Subsequent cohorts (B2 and B3) were given 10 and 20 mg/kg based on results from the previous cohorts in both Parts A and B. Cohort B4 is planned with a dose level of 40 mg/kg based on data from Cohort A5.

The review of the PK data from Cohorts A1 through A4 and the first 2 cohorts of Part B confirmed that once daily (QD) dosing is adequate.

Part C consists of 3 open-label MAD dosing cohorts (same dose levels as Cohorts B2, B3, and B4) in healthy subjects. Cohort C1 was conducted at the same time as Cohort B3 using the same dose (10 mg/kg) as Cohort B2. Cohort C2 was conducted after all subjects in Cohort B3 completed the study (minus the EOS Visit) and used the same dose (20 mg/kg) as Cohort B3; data from Cohort C1 were also considered before starting Cohort C2. Cohort C3 will run concurrently with Cohort B4 and use the same dose (40 mg/kg); data from Cohort C2 were also considered before starting Cohort C3. Within each Part C cohort, all 4 subjects will be treated with AT-007. Subjects will have a lumbar puncture on Day 7 to collect CSF for the measurement of AT-007 with the exact timing of the lumbar puncture based on PK data from Part B. Otherwise, the subjects in Part C have the same schedule as the subjects in Part B (minus randomization).

Before the study proceeded to Part D (SAD and MAD in subjects with CG), safety data from Cohorts A1 through A4 in Part A and the first 2 cohorts in Part B were evaluated by the SRC and all PK data from these cohorts were evaluated by the Sponsor.

Three dosing cohorts are planned for subjects with CG (Part D). The same subjects will receive both the single dose and the multiple doses. Within each cohort of 6 subjects, 4 subjects will be randomly assigned to AT-007 and 2 subjects will be randomly assigned to placebo. Following a single dose of study drug (AT-007 or placebo), there will be a 5-day washout. Subjects who tolerate the single-dose will receive 1 daily dose of the same study drug (AT-007 or placebo) for 27 consecutive days. The decision of whether each individual subject can start multiple dosing

will be made by the Investigator in consultation with the Sponsor. **No subject in Part D can start multiple dosing without explicit agreement from the Sponsor.** Subjects will complete the 27 days of treatment and the associated PK, PD, and safety assessments through the 2 days after the MAD portion and then have an EOS Visit at 28 days after the last dose.

The starting dose for Part D (i.e., for Cohort D1) was based on results from Part A (Cohorts A1 through A4) and Cohorts B1 and B2 and at 5 mg/kg was lower than the dose for Cohort B2 (10 mg/kg). The dose for Cohort D2 (20 mg/kg) was based on results from these cohorts plus Cohorts B3 and D1; results for Cohort C1 were also considered. The dose for Cohort D3 will be based on results from all cohorts in Parts A and B and Cohorts D1 and D2 and will not be higher than the dose for Cohort B4.

Before the study proceeds to Part E (SAD and MAD in subjects with GALK-deficient Galactosemia), safety data from all completed cohorts in Parts A, B, and D of the study will be evaluated by the SRC and all PK data from these cohorts will be evaluated by the Sponsor. The starting dose for Part E will not be higher than the highest acceptable dose in Part D at the time of starting Part E (after all subjects complete Cohorts D1 and D2 but may be before, during, or after Cohort D3). The dose for subsequent cohorts (if any) in Part E will be based on results from the previous cohort(s) in Part E.

One to 3 dosing cohort are planned for subjects with GALK-deficient Galactosemia (Part E). The same subjects will receive both the single dose and the multiple doses. Within each cohort of 6 subjects, 4 subjects will be randomly assigned to AT-007 and 2 subjects will be randomly assigned to placebo. Following a single dose of study drug (AT-007 or placebo), there will be a 5-day washout. Subjects who tolerate the single-dose will receive 1 daily dose of the same study drug (AT-007 or placebo) for 27 consecutive days. The decision of whether each individual subject can start multiple dosing will be made by the Investigator in consultation with the Sponsor. **No subject in Part E can start multiple dosing without explicit agreement from the Sponsor.** Subjects will complete the 27 days of treatment and the associated PK, PD, and safety assessments through the 2 days after the MAD portion and then have an EOS Visit at 28 days after the last dose.

Notes for Parts D and E: The overall number of subjects per cohort may be increased up to 8 subjects to address any potential lost-to-follow-up among subjects treated with either placebo or AT-007. Subjects treated with study drug (placebo or AT-007) in a cohort may be randomized to treatment in another cohort (separate consent required) within the same Part (assuming no safety or tolerability issues in the prior cohort) as long as there is a washout period of ≥ 5 days between the last dose in a cohort and the first dose in the next cohort.

The dose for the first cohort of the Part D Extension (DE1) will be 20 mg/kg/day based on acceptable SAD and MAD safety and PK data from Cohort D2. After SRC review of all SAD and MAD data and Sponsor review of PK and galactitol data for Cohorts D1 through D3, a second cohort of the Part D Extension (DE2) may be initiated to evaluate a dose >20 mg/kg/day if this dose was well tolerated in the SAD and MAD portions of the study in both healthy volunteers and subjects with CG.

In Part D Extension, within each cohort of up to 28 subjects, subjects will be randomly assigned in a 3:1 to AT-007 and placebo. Subjects will receive 1 daily dose of the same study drug (AT-007 or placebo) for 90 consecutive days. Subjects will complete the 90 days of treatment

and the associated PK, PD, and safety assessments through the day after the last dose and then have an EOE Visit at 28 days after the last dose. The EOE Visit will not be required for subjects who transition to a separate Open-Label Extension Study. For these subjects the study completion will be the completion of the Treatment Period at Day 91.

For all its parts (A, B, C, D, E, and D Extension), the study consists of a Screening Period (28 days [Day -28 to Day -1] in Parts A, B, and C; 40 days [Day -40 to Day -1] in Parts D and E; and Day -60 to Day -1 in Part D Extension for de novo subjects who did not participate in Part D and subjects whose last visit in Part D was >60 days before Day 1 in the Part D Extension]), a period of study treatment and associated assessments, and an EOS Visit (28 days after the last dose of study drug) (for Part D Extension, the visit at 28 days after the last dose is called the end of extension [EOE] Visit). Part D Extension de novo subjects may also participate in optional prescreening. Subjects will be randomized and receive the first dose of study drug on Day 1. At a minimum, subjects will remain at the clinical research unit (CRU) through 24 hours after the first dose. Subjects in Part A will have 1 in-clinic stay during the Treatment Period with the single dose taken in the CRU. Subjects in Parts B and C will have 1 in-clinic stay with all 7 doses taken in the CRU. Subjects in Parts D and E will have 3 in-clinic stays with most doses taken at home. Subjects in Part D Extension will have 2 in-clinic stays and monthly visits (home health or in-clinic) with most doses taken at home. Subjects who withdraw or are withdrawn from the study after taking study drug will not be replaced.

The Schedules of Assessments for Parts A, B, C, D, E, and D Extension are provided in [Appendix A](#) (Part A), [Appendix B](#) (Part B), [Appendix C](#) (Part C), [Appendix D](#) (Part D), [Appendix E](#) (Part E), and [Appendix F](#) (Part D Extension), respectively.

At selected time points during all parts of the study, all subjects will have the following:

- Assessment of AEs
- Blood and urine samples collected for routine safety laboratory assessments
- Physical examinations, assessment of vital signs, and ECGs
- Pregnancy tests (all females at screening and females of childbearing potential subsequently)
- Blood samples collected for PK

For subjects enrolled in selected cohorts in Parts A and D (Cohorts A4, A5, and D3), urine samples will be collected at selected time points after the single dose for the assessment of AT-007.

Subjects in Part C will have a lumbar puncture on Day 7 after the last dose to collect CSF for measurement of AT-007. The timing of the lumbar puncture relative to the last dose will be based on the PK data from completed cohorts in Part B. The intent is for the lumbar puncture to be taken close to the time of the maximum observed concentration (T_{max}) of AT-007 after the last dose.

During Part D, at selected time points, subjects will have blood samples taken for the assessment of GALT activity in red blood cells, GALT gene analysis, and aldose reductase activity; these assessments will also be done for Part D Extension subjects who did not participate in Part D but will not be repeated for those who did participate in Part D. Also, subjects in both Part D and

Part D Extension will have blood samples taken for the assessment of galactose and its metabolites, and subjects in Part D will also have urine collected for the assessment of galactitol.

During Part E, at selected time points, subjects will have blood samples taken for the assessment of GALK activity in red blood cells, GALK gene analysis, aldose reductase activity, as well as galactose and its metabolites and urine collected for the assessment of galactitol.

Within each multi-cohort part (A, B, C, and D [and E, if applicable]) of the study, in the subsequent cohorts after the first cohort, the dose may be increased, decreased, or repeated. The SRC will review safety (including AE, laboratory, physical examination, vital signs, and ECG data) through Days 3, 8, 8, 12, and 12 during Parts A, B, C, D, and E, respectively, for each cohort and provide a recommendation for the next cohort as needed. If there is a second cohort in Part D Extension, the dose will be higher than 20 mg/kg and depend on the results for that dose in healthy subjects and subjects with CG in Part D.

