Safety and PK data from Cohorts A1 through A5, Cohorts B1 through B3, and Cohorts C1 and C2 were evaluated before deciding to start Cohorts B4 and C3 (MAD with lumbar puncture) simultaneously at the same dose (40 mg/kg).

Safety and PK data from Cohorts A1 through A4 and Cohorts B1 and B2 were evaluated before Part D (SAD and MAD in subjects with CG) was allowed to start. In addition to safety data through Day 12 and at least single dose PK and galactitol results from the previous cohort(s) within Part D and safety and PK data from Cohort B3 were evaluated before Cohort D2 was allowed to start. Safety and PK data from Cohort B4 will be evaluated before Cohort D3 will be allowed to start.

Safety data through Day 12 and at least single dose PK and galactitol results from all completed cohorts within Part D (at least Cohorts D1 and D2 [possibly Cohort D3, depending on timing]) will be evaluated before Cohort E1 will be allowed to start. The starting dose for Part E will not be higher than the highest acceptable dose in Part D at the time that Part E starts. In case of multiple cohorts in Part E, safety data through Day 12 and at least single dose PK and galactitol results from previous cohort(s) within Part E will be evaluated before subsequent cohorts in Part E will be allowed to start.

Safety and PK data from Cohort D2 were evaluated before deciding the dose (20 mg/kg) for Cohort DE1 (Part D Extension). In case of a second cohort in the Part D Extension, safety data through Day 12 and at least single dose PK and galactitol results from all completed cohorts within Part D (including Cohort D3) and safety and PK data for Cohorts A5 and B4 will be evaluated before deciding upon a dose.

At each dose escalation decision, the SRC will recommend proceeding or not proceeding to the next cohort as well as the dose level for AT-007. The AT-007 dose level may be increased, decreased, or repeated from one cohort to the next.

Parts A, B, and C will be conducted at a single CRU. The Principal Investigator (or designee) at that study center will be part of the SRC during Parts A, B, and C.

Parts D, E, and D Extension will be conducted at multiple centers. The Principal Investigators (or designees) will be part of the SRC during Parts D, E, and D Extension.

At minimum, the SRC will meet and review data at the following times:

- Review of safety data through Day 3 for the following cohorts to determine whether to proceed with the next cohort and at what dose level:

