 - Cohort A1
 - Cohort A2
 - Cohort A3
 - Cohort A4 (At this SRC meeting, a starting dose level for Part B was recommended and subsequently confirmed after Sponsor review of all PK data from Cohorts A1 through A4.)
 - Cohort A5 (At this SRC meeting, a dose level for both Cohorts B4 and C3 was recommended and subsequently confirmed after Sponsor review of all PK data from Cohorts A1 through A5.)
- Review of safety data through Day 8 for the following cohorts to determine whether to proceed with the next cohort and at what dose level:
 - Cohort B1
 - Cohort B2 (At this SRC meeting, starting dose level[s] for Part C and Part D were recommended and subsequently confirmed after Sponsor review of all PK data from Cohorts A1 through A4 and Cohorts B1 and B2.)
 - Cohort B3/C1 (At this SRC meeting, a dose level for Cohorts C2 and D2 was recommended and subsequently confirmed after Sponsor review of all PK data from Cohorts A1 through A4 and Cohorts B1 through B3 and Cohort C1 as well as single dose PK and galactitol data from Cohort D1 and SRC review of safety data from Cohort D1.)
 - Cohort C2
 - Cohort B4/C3 (At this SRC meeting, a dose level for Cohort D3 will be recommended and require confirmation [or change] after Sponsor review of all PK data from all of Parts A and B as well as single dose PK and galactitol data from Cohorts D1 and D2. Note: Because Cohorts A5, B4, and C3 are new or newly opened, SRC review of safety from Cohorts D1 and D2 was already done by the time Cohort A5 was added to the protocol.)
- Review of safety data through Day 12 (Study Day 12, not the 12th day of multiple dosing) for the following cohorts to confirm whether to proceed with the next cohort and at what dose level:
 - Cohort D1

- Cohort D2
- Review of safety data through Day 12 (Study Day 12, not the 12th day of multiple dosing) for Cohort D3 (At this SRC meeting, a dose level for Cohort E1 may be recommended if Cohort E1 has not already started with a dose level not higher than that for Cohort D2. A dose level may also be recommended for Cohort DE2. Any recommended dose level requires confirmation [or change] after Sponsor review of all PK data for Parts A, B, C, and D as well as single dose galactitol data from Cohorts D1 through D3.)

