3.5. Dose Escalation/De-escalation

For Parts A, B, and C of the study (healthy subjects), safety and drug exposure will determine escalation or de-escalation. If the initial dose tested in Part A had not been well tolerated, the Sponsor may have chosen to de-escalate until a well-tolerated dose was identified. A careful analysis of available safety, laboratory evaluation, and drug PK data in healthy subjects was done to determine the starting dose for Part D in subjects with CG. A careful analysis of available safety, laboratory evaluation, and drug PK data in subjects with CG will determine the starting dose for Part E in subjects with GALK-deficient Galactosemia. The starting dose in Part E will not be higher than the highest acceptable dose used in Part D at the time of starting Part E. The starting dose in Part D Extension will be 20 mg/kg based on acceptable SAD and MAD safety and PK data from Cohort D2.

For Part D of the study (subjects with CG), safety, drug exposure, and biomarker analysis of galactitol will determine escalation or de-escalation. If the drug exposure in subjects with CG is similar to that seen in healthy subjects in Part A, the same or similar approach to dose escalation may be utilized. If there is any concern of altered drug exposure or drug clearance based on PK analysis after the single dose in the initial cohort of Part D, then alternative dose escalation to lower levels may be selected until the relationship between dose and exposure in subjects with CG is determined. Dose escalation may be stopped if an effect on galactitol (reduction in galactitol) is achieved, but it becomes apparent that higher drug exposure is not increasing reduction of galactitol or providing any additional benefit. If any tested dose is not well tolerated

while markedly reducing galactitol levels, lower dose levels may be tested until no/minimal reduction in galactitol levels is detected.

In case of multiple cohorts in Parts E, the dose escalation process will be the same as for Part D.

A second cohort of the Part D Extension (DE2) may be initiated to evaluate a dose higher than 20 mg/kg/day if this dose was well tolerated in the SAD and MAD portions of the study in both healthy volunteers and subjects with CG.

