The SRC will make recommendations to the Sponsor regarding dose escalation or de-escalation for each cohort based on the results from the previous cohort as described in [Section 3.4](#). The Sponsor will act upon this recommendation and inform the Investigator(s) and the IRB(s)/IEC(s).

The SRC will pay particular attention to DLTs defined as any AT-007-related AE or clinically relevant finding on laboratory tests, ECGs, vital signs, or physical examinations that, in the opinion of the Investigator and/or the SRC, precludes administering the dose to any subject and/or continuing to administer daily doses to the subject who experienced the event. Specific individual subject-level dose stopping criteria for hepatic and renal toxicity are described in [Appendix G](#) and [Appendix H](#). For DLTs, as well as fatal serious adverse events (SAEs) and life-threatening SAEs, breaking the blind will be considered and initiated (as needed) per SRC discussion and agreement.

Dose-escalation will be stopped and de-escalation initiated if:

- ≥ 2 subjects on AT-007 (B and C cohorts of the same dose level considered together) experience a DLT at any time through 24 hours after the last dose of study treatment
- Any subject on AT-007 has a fatal SAE or life-threatening SAE requiring urgent intervention at any time through 24 hours of the last dose of study treatment

The maximum tolerated dose (MTD) will be the dose level below the dose level at which one or more of the events listed above occurs.

Dose escalation within each part of the study will continue until the MTD is identified per the rules described earlier in this section or the SRC and/or Sponsor decide to stop dose escalation. Dose de-escalation, if initiated within any part of the study, will continue until the MTD is identified or the SRC and/or Sponsor decide to stop.

If the events outlined in the above MTD definition do not occur at any dose level in a study part, then the MTD will be the highest dose level in that study part.

If the events outlined in the above MTD definition occur at any given dose level, the Sponsor may decide to investigate a dose higher than the previously well-tolerated dose but lower than the dose at which one of the events outlined in the above MTD definition occurred.

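### The Safety Review Committee should be required to see accrued DE1 safety data before it opens the higher-dose 90-day cohort, DE2

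*Protocol*

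**What the plan says.** The note under Figure 2 (protocol Section 3.1) states "Cohort DE2 (start and dose level) are not dependent on results from Cohort DE1". The SAP repeats it under Figure 1. Section 3.1 adds that, for any second Extension cohort, "the dose will be higher than 20 mg/kg and depend on the results for that dose in healthy subjects and subjects with CG" (the latter from Part D). Section 3.5 agrees: a second cohort "may be initiated to evaluate a dose higher than 20 mg/kg/day if this dose was well tolerated in the SAD and MAD portions" in healthy volunteers and in subjects with classic galactosemia.

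For that decision Section 3.4 names safety through Study Day 12 and at least single-dose PK and galactitol results from the completed Part D cohorts. The sentence ends "including Cohort D3) and safety and PK data for Cohorts A5 and B4 will be evaluated before deciding upon a dose". Of the SRC meeting on Cohort D3, Section 3.4 says: "A dose level may also be recommended for Cohort DE2". DE1 appears in the list of SRC meetings only once, in an undated closing review that also covers DE2.

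Section 3.5 holds the stopping rule: at least two AT-007 subjects with a dose-limiting toxicity (DLT), or one fatal or life-threatening SAE on AT-007 that needs urgent intervention. On scope it says "Dose escalation within each part of the study will continue until the MTD is identified per the rules described earlier in this section", unless the SRC or Sponsor stops sooner. The MTD "will be the dose level below the dose level at which one or more of the events listed above occurs".

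**The concern.** DE2 is a higher dose than DE1 in the same part of the study, given for the same 90 days and mostly taken at home. In Parts A to E, results from one cohort feed the decision on the next. In the Extension the figure note sets the earlier cohort aside, and the list of data for the decision leaves it out.

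At stake is toxicity that appears only with longer dosing. Parts A to E stop at 27 consecutive daily doses. The 13-week rat and dog studies in Section 1.4 support 90-day dosing nonclinically, and Part D gives up to 27 daily doses at DE2's own level. Neither shows longer human exposure. A higher 90-day dose could open without anyone being required to look at data already in hand from the lower one.

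**Working it through.** The plan states no figure on this point, so the check is mainly a comparison of texts.

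**1. Data named for the DE2 decision.** Section 3.4 names Part D (including D3), A5 and B4. For the D3 meeting it adds Sponsor review of PK from Parts A, B, C and D and of single-dose galactitol from D1 to D3. Section 3.3.6 names all SAD and MAD data from D1 to D3. DE1 is in none of these.

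**2. The stopping rule.** Section 3.5 does not exempt the Extension. DE1 is at 20 mg/kg and DE2 must be above it, so a DE1 that met the rule would put the MTD below 20 mg/kg and bar DE2.

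**3. General provisions that could bring DE1 to the SRC.**
- Section 3.3: additional cohorts follow an SRC safety assessment and Sponsor confirmation. The data source is not given.
- Section 3.4: the SRC reviews safety from every cohort in every part. Review days are given for Parts A to E only.
- Section 3.4: AEs (with DLTs), laboratory tests, examinations, vital signs and ECGs are assessed before each escalation decision within a part. This lists kinds of data, not cohorts.
- Section 3.4: the meeting list is a minimum, and the Extension's investigators sit on the SRC.
- Section 3.5: SRC advice is given "for each cohort based on the results from the previous cohort as described in" Section 3.4, which does not name DE1 for DE2.
- Section 3.5: for DLTs, breaking the blind is a matter for SRC discussion.
- SAP 7.14: SRC review covers the Extension by name, again with days for Parts A to E only.

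Each allows a look at DE1 and some prompt one. None ties accrued DE1 data to the opening of DE2.

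**4. Other safety reporting.** SAEs go to the Sponsor immediately (Section 8.3), and specified hepatic and renal findings within 24 hours (Appendices G and H). The Sponsor is unblinded in the Extension (Section 5.2) and sits on the SRC. Other AEs are reported regularly or as the Sponsor specifies (Section 8). A DLT need not be serious, so what is least protected is a non-serious DLT outside those triggers.

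**5. Exposure that only DE1 can show.** The longest continuous dosing in Parts A to E is 27 days; the Extension is 90.
- 27/90 = 30%
- 90 − 27 = 63, and 63/90 = 70%

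At nominal days the three on-treatment laboratory draws (Days 30, 60 and 90) follow at least 29, 59 and 89 daily doses. With the two-day window, the earliest Day 30 visit follows 27. Using 27 favours the plan: the Study Day 12 cut in Section 3.4 covers only 7 consecutive daily doses (Days 6 to 12).

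**6. Size of DE1 with two cohorts.** Protocol Table 1 allows at least 8 subjects per cohort and 28 in total, so DE1 has 8 to 28 − 8 = 20 subjects.
- On AT-007 at 3:1: 8 × 3/4 = 6 to 20 × 3/4 = 15
- Two DLTs: 2/15 = 13.3% to 2/6 = 33.3% of them

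The SAP's smaller total of 16 gives two cohorts of 8, hence 6 on AT-007. The number past 27 doses when DE2 is decided is not stated and could be anything from 0 to 15.

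**The case against.** The strongest answer is that the note is a figure legend about prerequisites. It defines its arrows as showing which data must exist before a cohort can start, so independence from DE1 most naturally means that DE1 need not come first. The same legend says the galactosemia parts do not depend on Part C. Yet C1 results were considered for the D2 dose (Section 3.1), and Part C PK is among the data the Sponsor reviews before a dose recommended at the D3 meeting is confirmed (Section 3.4). This reading is fair and it stands.

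A reader might go further and infer that the note waives the stopping rule for DE1, or flatly contradicts Section 3.5. The documents support neither. The rule applies within each part without exception, and a cohort that is not a prerequisite can coexist with a rule triggered by events. The previous-cohort wording in Section 3.5 does not create a contradiction either, because it defers to Section 3.4. Basing the DE2 dose on Part D, A5 and B4 is a deliberate and legitimate choice.

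It is also fair that the SRC's general duties, its discussion of DLTs, the investigators' seats and the unblinded Sponsor make it likely that a DE1 problem would be noticed. What remains is that none of these names DE1 or fixes when it is looked at relative to DE2.

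**Conclusion.** The concern holds as a missing requirement: followed as written, the plan lets DE2 open without accrued DE1 safety being put before the SRC. The data concerned are the only human data in this study, before DE2, beyond 27 consecutive daily doses: 63 of the 90 planned doses (70%), in at most 6 to 15 subjects on AT-007.

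The practical effect is modest. The stopping rule still binds, much would reach the Sponsor by other routes, DE2 is optional, and few DE1 subjects may be past dose 27 at an early decision. The conclusion assumes that two cohorts are run at the Table 1 sizes and that DE1 has begun when DE2 is considered, as sequential cohorts imply. It rests on no assumed DLT rate; the documents give none. This is a minor point and a cheap improvement.

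**What to change.** In protocol Section 3.4, add DE1 safety accrued to date to the data the SRC reviews before DE2 opens: AEs, DLT count, laboratory data, and the number of subjects past 27 consecutive daily doses.

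Reword the note under protocol Figure 2 and SAP Figure 1 to: *DE1 need not be complete before DE2 starts and the DE2 dose is based on Part D, A5 and B4, but the Section 3.5 stopping rule in DE1 applies to DE2.*

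The cost is one addition to Section 3.4, one sentence in each figure note, and one DE1 safety data cut for the meeting that decides on DE2. That cut may be sparse if the meeting is early. DE2 does not have to wait for DE1 to finish, and the basis for its dose is unchanged.
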